6.2 PREPARATION/HANDLING/STORAGE/ACCOUNTABILITY

6.2.1 ACQUISITION AND ACCOUNTABILITY

IFx-Hu2.0, the drug product, is composed of pAc/*emm55*, an immunomodulator, complexed with Polyplus in vivo-jetPEI® (linear polyethylenimine), a transfection reagent, and dextrose, a complex stabilizer. After compounding IFx-Hu2.0 per the Pharmacy Manual at the Investigational Drug Services (IDS) pharmacy, each vial contains 0.2 mg of pAc/*emm55* in 0.4 mL of solution.

The sponsor provides IFx-Hu2.0 as a vaccine kit with finished drug product preparation instructions and consumables (except for the final clinical site-supplied syringe for direct patient care).

To request vaccine kits delivered to the site, the site personnel should complete the investigational product (IP) requisition form (Appendix A) and email it to [contact]. Whenever the sponsor distributes IP to a site, a sponsor-initiated IP distribution form will accompany the order and require the dated signature of the receiving site personnel.

Any unused IFx-Hu2.0 vaccine kits will be reverse-distributed by the site to the sponsor under the following conditions:

- a) A vaccine kit has met its retest date,
- b) The participation of the primary investigator at the clinical site has been discontinued,
- c) The participation of the clinical site has been discontinued, or
- d) The trial has been completed.

To reverse distribute the unused vaccine kits from the site to the sponsor, site personnel should complete the IP reverse distribution form (Appendix B of the Pharmacy Manual), schedule delivery with the carrier noted on this form, copy the completed form for his or her own records and include the original, completed form in the delivery to the sponsor.

6.2.2 FORMULATION, APPEARANCE, PACKAGING, AND LABELING

The sponsor provides the investigational product (IP) as a vaccine kit with drug product preparation instructions and consumables (except for the final clinical site-supplied syringe for direct patient care).

Up-to-date information regarding the IP formulation, appearance, packaging, and labeling can be found in the Pharmacy Manual.

6.2.3 PRODUCT STORAGE AND STABILITY

Store the IFx-Hu2.0 vaccine kits and their contents refrigerated at 2 – 8°C.

The prepared drug product must be administered intralesionally within 4 hours from the time of complexing and final incubation.

6.2.4 PREPARATION

Store all IFx-Hu2.0 vaccine kits and their contents refrigerated at 2 – 8°C. Remove vaccine kits from the refrigerator as needed when ready to prepare drug product. One vaccine kit makes a fixed dose for one intralesional injection. Perform each step aseptically in a primary engineering control (PEC) (i.e., a vertical laminar airflow workbench in an International Organization for Standardization [ISO] 5 environment) whenever feasible. Follow the current official United States Pharmacopeia (USP) <797> chapter as well as the instructions in the Pharmacy Manual to prepare one single-dose vial of IFx-Hu2.0.

6.3 STUDY INTERVENTION COMPLIANCE

To document study drug administration, vial identification information, time of administration, and any notes regarding the injection(s) will be documented by the administering investigator on the drug administration case report form. Study drug compliance will be reviewed by the study monitors and the principal investigator.

6.4 CONCOMITANT THERAPY

For this protocol, a prescription medication is defined as a medication that can be prescribed only by a properly authorized/licensed clinician. Medications to be reported in the Case Report Form (CRF) are concomitant prescription medications, over-the-counter medications, and supplements taken during participation and over 90 days prior to enrollment.

7 STUDY INTERVENTION DISCONTINUATION AND PARTICIPANT DISCONTINUATION/WITHDRAWAL

7.1 DISCONTINUATION OF STUDY INTERVENTION

If a clinically significant finding is identified (including, but not limited to changes from baseline) after enrollment, the investigator or qualified designee will determine if any change in participant management is needed. Any new clinically relevant finding will be reported as an adverse event (AE). Subjects with treatment-related toxicity will be followed for the ongoing drug-related adverse events until resolved, return to baseline, deemed irreversible by the treating physician, the subject has been properly referred to an appropriately licensed practitioner for further evaluation and treatment, or until the subject is lost to follow up, withdrawal of study consent, removal of the subject from the trial by the treating physician, or start of a subsequent anti-cancer therapy.

The data to be collected at the time of study intervention discontinuation will include the following:

1. Concomitant medications
2. ECOG performance status
3. Physical exam, including vital signs, height, weight
4. Laboratory tests
 - 4.1. Hematology: CBC - hemoglobin, hematocrit, white blood cells (WBC) with differential count, platelet count; blood clotting tests: prothrombin time (PT) and activated partial thromboplastin time (aPTT)
 - 4.2. Biochemistry: CMP - glucose, calcium, albumin, total protein, sodium, potassium, CO2, chloride, BUN, creatinine, total bilirubin, alanine aminotransferase (ALT), aspartate aminotransferase (AST), alkaline phosphatase (ALP), lactate dehydrogenase (LDH), Thyroid tests (TSH and FT4)
 - 4.3. Urinalysis: UA with microscopic evaluation
 - 4.4.
 - 4.5. Anti-double-stranded DNA (anti-dsDNA) antibody test
 - 4.6. Anti-DNase B Titer, Serum
5. Adverse event recording per CTCAE v5.0
6. Tumor lesion measurement (longest diameter)
7. Serum pregnancy tests for females of reproductive potential
8. 40 mL of blood for immune response evaluation
 - 8.1. Tumor biopsy for pathological response (final)

7.2 PARTICIPANT DISCONTINUATION/WITHDRAWAL FROM THE STUDY

Participants are free to withdraw from participation in the study at any time upon request.

An investigator may discontinue or withdraw a participant from the study for the following reasons:

1. Pregnancy

2. Significant study intervention non-compliance
3. If any clinical adverse event (AE), laboratory abnormality, or other medical condition or situation occurs such that continued participation in the study would not be in the best interest of the participant
4. Disease progression
5. If the participant meets an exclusion criterion or fails to meet an inclusion criteria (either newly developed or not previously recognized) that precludes further study participation

The reason for participant discontinuation or withdrawal from the study will be recorded on the case report form (CRF). Subjects who sign the informed consent form but do not receive the study intervention may be replaced. Subjects who sign the informed consent form, and receive the study intervention, and subsequently withdraw, or are withdrawn or discontinued from the study will be replaced.

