2.3 RISK/BENEFIT ASSESSMENT

2.3.1 KNOWN POTENTIAL RISKS

IFx-Hu2.0 primes the immune system to a broad array of patient-specific tumor antigens. When breaking tolerance to tumor-associated antigens, which are 'self' antigens, there is a possibility of inducing some form of autoimmunity. Since efficacy and adverse events of immunotherapies are in general mediated by the same underlying pathways and mechanisms, there may be an increased risk of autoimmunity with immunotherapies such as IFx-Hu2.0. Patients receiving immunotherapies have been reported to experience mild pyrexia, cutaneous reactions, diaphoresis, rigor, tachypnea and hypotension.

In the IFx-Hu2.0 monotherapy phase I trial (NCT03655756), eight patients were screened, seven patients were enrolled and treated, and six patients were evaluable for the primary endpoint. There was one screen failure and one death unlikely related to the study drug as determined by the principal investigator. The primary outcome measure of this trial was the rate of DLTs defined as the rate of grade 3 to 5 treatment-related adverse events (AEs) that were deemed unacceptable toxicities by the principal investigator. No grade 3 to 5 treatment-related adverse events (AE) per CTCAE v5.0 were reported (Grade 1 – mild; Grade 2 – moderate). Table 2 and Table 3 reflect all AEs observed in this trial.

Table 2 Treatment-Related AEs based on preliminary data from the IFx-Hu2.0 monotherapy phase I trial (NCT03655756)

All Treatment-Related Adverse Events (Attribution: possible to definite), n=6	Number of Patients (%)	Severity
Injection site reaction	4 (67%)	Mild to Moderate
Tumor hemorrhage	2 (33%)	Mild to Moderate
Tumor pain	1 (17%)	Moderate
Erythema	1 (17%)	Mild
Paresthesia	1 (17%)	Mild
Back pain	1 (17%)	Mild
Lymphocyte count decreased	1 (17%)	Mild
Muscle cramp	1 (17%)	Mild
Pruritus	1 (17%)	Mild
Total	6 (100%)	

Table 3 All AEs based on preliminary data from the IFx-Hu2.0 monotherapy phase I trial (NCT03655756)

All Adverse Events, n=7	Number of Patients (%)	Severity
Injection site reaction	4 (67%)	Mild to Moderate
Tumor hemorrhage	2 (33%)	Mild to Moderate
Hypertension	2 (33%)	Mild to Severe
Erythema	1 (17%)	Mild
Paresthesia	1 (17%)	Mild
Back pain	1 (17%)	Mild
Lymphocyte count decreased	1 (17%)	Mild
Muscle cramp	1 (17%)	Mild
Pruritus	1 (17%)	Mild
Anorexia	1 (17%)	Mild
Dry mouth	1 (17%)	Mild
Insomnia	1 (17%)	Mild
Flatulence	1 (17%)	Mild
Lymphedema	1 (17%)	Mild
Constipation	1 (17%)	Moderate
Tumor pain	1 (17%)	Moderate

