5.2 EXCLUSION CRITERIA

An individual who meets any of the following criteria will be excluded from participation in this study:

1. Concurrent participation in any other clinical trial
2. Inability to consent for self
3. Lesions on scalp with bone erosions must not be selected as injection sites for IFx-Hu2.0

4. Life expectancy of fewer than 24 weeks at the time of screening
5. Prior systemic anti-cancer treatment within three weeks from start of treatment (Day 0)
6. Treatment with any investigational product within the three weeks preceding injection
7. Concurrent chemotherapy or biological therapy. Concurrent radiotherapy is allowed as long as it is not the same site as the injected lesion.
8. Current treatment with systemic immunosuppressive corticosteroid (greater than 10 mg of daily prednisone) doses or other immunosuppressants such as those needed for solid organ transplants. Medications needed to treat conditions such as reactive airway disease are not excluded.
9. Is pregnant, breastfeeding, or expecting to conceive or father children within the projected duration of the trial, starting with the pre-screening or screening visit through 26 weeks after the last dose of trial treatment
10. Immunizations for encapsulated bacteria were not given for patients who have undergone a splenectomy
11. Serious underlying medical or psychiatric conditions, active infections requiring the use of antimicrobial drugs, or active bleeding that would make the subject unsuitable or unable to participate in the study
12. Active Human Immunodeficiency Virus (HIV)/Acquired Immunodeficiency Syndrome (AIDS) or Hepatitis B/C. Patients with treated HIV/AIDS or Hepatitis B/C with no evidence of active infection may be enrolled
13. History of organ allograft transplantation
14. Presence of any uncontrolled and significant medical or psychiatric condition which would interfere with trial safety assessments

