6.1.2 DOSING AND ADMINISTRATION

The amount of drug administered to the participant is 0.1mg injected into a single lesion. IFx-Hu2.0 must be administered within 4 hours of constitution (see Investigator's Brochure section 3.3).

IFx-Hu2.0 is intended for intralesional (i.e. cutaneous, subcutaneous, or lymph nodal) injection. All participants will be monitored for 30 minutes after injection for any immediate adverse events. Participants must abstain from caffeine- or xanthine-containing products (e.g., coffee, tea, cola drinks, and chocolate) for 6 hours and abstain from alcohol for 24 hours before the administration of IFx-Hu2.0.

Administration

1. Avoid placing fingers near the lesion being injected to prevent needlesticks.
2. Use a single insertion point for each lesion.
3. Inject evenly throughout the lesion on multiple tracks, pulling the needle back after injecting a portion of the drug without withdrawing it from the lesion, then rotating it radially on another track until the entire lesion is treated. If the lesion is resistant to drug injection, apply slow, steady pressure, moving the needle slightly as needed. Local anesthetic should not be injected into the lesion or the surrounding tissue, since it may alter pH and therefore drug stability.
4. Withdraw the needle slowly to reduce the risk of drug leakage.
5. Clean the injection site and surrounding area with an alcohol pad.

A single dose (0.1mg) will be used in this trial and at a single timepoint, therefore no dose escalation or reduction is proposed.

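### Withdrawal reason 5 has no pre-dose limit: a dosed participant can be removed and replaced inside the 4-week DLT window, and the stopping boundary, and possibly the feasibility count, can miss that participant's DLT

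*Protocol*

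**What the plan says.** Protocol 7.2 opens its list with "An investigator may discontinue or withdraw a participant from the study for the following reasons". Reason 5 begins "If the participant meets an exclusion criterion or fails to meet an inclusion criteria (either newly developed or not previously recognized" and carries a qualifier: "either newly developed or not previously recognized) that precludes further study participation". Reason 3 separately allows withdrawal for an adverse event or laboratory abnormality when continuing is not in the participant's best interest. The section ends by stating that participants who receive the intervention and "subsequently withdraw, or are withdrawn or discontinued from the study will be replaced".

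Protocol 6.1.2 fixes the exposure: "A single dose (0.1mg) will be used in this trial and at a single timepoint".

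Some entry criteria describe conditions that toxicity, or its treatment, could produce:
- Exclusion 11 (Protocol 5.2): "active infections requiring the use of antimicrobial drugs, or active bleeding that would make the subject unsuitable or unable to participate in the study".
- Exclusion 8 (Protocol 5.2): "Current treatment with systemic immunosuppressive corticosteroid (greater than 10 mg of daily prednisone) doses".
- Inclusion 7 and 11 (Protocol 5.1): the ECOG limit and the lymphocyte minimum.

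The earlier trial (Protocol 2.3.1, Table 2) lists "Tumor hemorrhage" in 2 of 6 patients and a decreased lymphocyte count in 1 of 6, both as treatment-related.

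On counting and follow-up:
- The boundary in Protocol 9.4.2 compares DLTs with patients who have completed, or full, follow-up.
- Protocol 5.5 aims for 100 evaluable patients and does not define the term.
- Feasibility is 80 of 100 in Protocol 3 and 9.4.1, and 85 of 100 in the Protocol synopsis and SAP 2.2.1. Neither definition says how a dosed leaver counts.
- SAP 3.2.1 reports the overall DLT rate on everyone dosed, and SAP 3.4 imputes nothing.
- Protocol 8.2.4 collects non-serious AEs for 7 days and SAEs for 30 days after the last day of participation.
- Protocol 7.1 and 8.1 list removal by the treating physician among the points that end follow-up of ongoing toxicity.

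**The concern.** After Day 0 there is no further treatment to stop, so withdrawal ends only observation. Reasons 3 and 5 let an investigator who knows the treatment and sees the emerging events end that observation inside the 4-week DLT window. Replacement then follows automatically.

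A participant who leaves with a low-grade event that later worsens may never be recorded as a DLT. A participant who leaves after a DLT has been recorded may still not enter the boundary, because follow-up was not completed. If only completers make up the 100 for feasibility, the same participant drops out there too and is replaced by someone new. Losses that are commoner among DLT patients make the treatment look safer. They weaken the stopping rule and raise the chance of declaring feasibility.

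**Working it through.** **1. Which events can go unrecorded after exit.** The DLT window runs to Day 28 (4 weeks, Protocol 9.2). For exit on Day d, Protocol 8.2.4 gives:
- SAEs: collected to Day d + 30. Even at d = 0 this is Day 30, past Day 28, so there is no gap.
- Non-serious AEs: collected to Day d + 7. The gap is 28 − (d + 7) = 21 − d days when d is below 21. Exit on Day 7 leaves Days 14 to 28 uncovered.

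The exposed event is therefore a non-serious, related event of grade 3 or higher that arises more than 7 days after exit. Worsening of an ongoing event is also exposed where removal ends toxicity follow-up (7.1, 8.1). On that point 8.2.4 says instead that events are followed to resolution or stabilisation, so the sections need reconciling.

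**2. Reproducing the boundary.** Take b_n as the smallest r with P(Bin(n, 0.2) ≥ r) ≤ 0.008340. All 100 printed values match. An exact binomial recursion, checking after every patient, gives:

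| True DLT rate | Crossing, printed | Crossing, exact | E[N], printed | E[N], exact |
|---|---|---|---|---|
| 0.20 | 0.0497 | 0.0490 | 96.58 | 96.60 |
| 0.30 | 0.6116 | 0.6137 | 67.08 | 67.10 |
| 0.40 | 0.9883 | 0.9878 | 29.65 | 29.59 |

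The small gaps go both ways and look like simulation error in the printed table (an inference).

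**3. Leavers dropped and replaced.** Let p be the true DLT rate and f the share of DLT patients who leave uncounted. The documents give no f; 0 to 0.3 is an assumption. Per dosed participant, p(1 − f) is a counted DLT and pf is a DLT patient who is dropped. The rate among those counted is

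q = p(1 − f) / (1 − pf).

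Example: p = 0.30, f = 0.2 gives 0.24 / 0.94 = 0.2553.

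The recursion was rerun at q. Feasibility, if only completers count, is P(Bin(100, q) ≤ 20) for the 80 threshold and P(Bin(100, q) ≤ 15) for the 85 threshold.

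| f | q (p = 0.30) | Boundary crossing | q (p = 0.25) | P(≥ 80 DLT-free) | P(≥ 85 DLT-free) |
|---|---|---|---|---|---|
| 0 | 0.3000 | 0.614 | 0.2500 | 0.149 | 0.011 |
| 0.1 | 0.2784 | 0.443 | 0.2308 | 0.275 | 0.032 |
| 0.2 | 0.2553 | 0.273 | 0.2105 | 0.455 | 0.083 |
| 0.3 | 0.2308 | 0.139 | 0.1892 | 0.665 | 0.193 |

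**4. The SAP's rate on all dosed participants.** A leaver stays in this denominator, and a DLT recorded before exit stays in the numerator. Only DLTs that are never observed are lost. If their share is w (also not given), the expected rate is p(1 − w): for p = 0.20, 0.20 × 0.90 = 0.18 at w = 0.10 and 0.20 × 0.75 = 0.15 at w = 0.25.

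**The case against.** Several points on the other side stand.

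- **Reason 5 is narrower than a quick reading suggests.** The power is discretionary, and the criterion must preclude further participation. Exclusion 11 is limited to bleeding or infection that makes the participant unsuitable or unable to take part. The organ-function limits in inclusion 10 refer to screening tests before Day 0. A low count or a steroid course after the injection need not prevent a Week 4 visit. However, the plan does not say which criteria preclude participation once the only dose has been given, so the investigator decides.
- **Reason 3 already allows withdrawal for toxicity.** Changing reason 5 alone would leave that exit open. Reason 3 does require a best-interest judgement, which reason 5 does not. The fix has to cover both.
- **Much is still captured.** AEs are documented at early termination, with examination, laboratory tests and ECG in the Schedule of Activities. SAEs are covered for the whole window. A reader might infer that withdrawal lowers the SAP's reported DLT rate in general. It does not: that rate keeps every dosed participant and every DLT recorded before exit.
- **Toxicity of this kind is possible, not expected.** In the earlier trial the haemorrhage was mild to moderate, the lymphocyte decrease was mild, and no related grade 3 to 5 event was reported. At a true DLT rate of 0.05, both feasibility thresholds are met with probability about 1.00 at f = 0 and at f = 0.3.

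A reader might also apply p(1 − f) to the boundary, which gives larger shifts (crossing 0.38, 0.18 and 0.07 at a true rate of 0.30). That formula keeps the leaver in the denominator as a non-event. The boundary counts only completed follow-up and leavers are replaced, so q is the matching formula.

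**Conclusion.** The concern holds in a limited form and should be fixed. Reason 5 applies after the only dose. Together with reason 3, mandatory replacement and a boundary restricted to completed follow-up, it lets a dosed participant's DLT go uncounted. The boundary is the clearest exposure. The feasibility count is exposed only if its 100 means completers, which the plan leaves open. The SAP's rate on all dosed participants is exposed only to unobserved non-serious events of grade 3 or higher and to worsening after follow-up ends.

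With f between 0.1 and 0.3, crossing at a true rate of 0.30 falls from 0.614 to between 0.443 and 0.139. At 0.25, the chance of meeting the 80 threshold rises from 0.149 to between 0.275 and 0.665.

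These figures rest on three assumptions: the value of f, a literal reading of completed follow-up, and exit only among DLT patients. If patients without a DLT left at the same rate, q would equal p and there would be no shift. The figures are illustrations, not estimates. The documents do not support the inference that removal is required, that it is likely, or that reason 5 alone causes the problem.

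**What to change.** 1. **Protocol 7.2.** Limit reason 5 to the period before the Day 0 injection. After it, record a newly developed criterion as an adverse event where it is one, and a previously unrecognised ineligibility as a protocol deviation. Neither should end follow-up or trigger replacement.
2. **Protocol 7.2, with 7.1, 8.1 and 8.2.4 aligned.** For any dosed participant withdrawn by the investigator for any reason, including reason 3, continue DLT ascertainment to Week 4, subject to consent. This concerns data collection only and leaves clinical care of the event unchanged.
3. **Protocol 9.4.2 and the feasibility definition in both documents.** State that every dosed participant counts, that a DLT counts when it occurs even if follow-up is incomplete, and that replacements are added to those who leave and do not substitute for them.

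The cost is a few sentences, some follow-up contact with withdrawn participants, and a denominator slightly above 100 dosed participants. Participants treated despite ineligibility stay in follow-up, but they are already in the Safety Analysis Dataset.

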5.5 STRATEGIES FOR RECRUITMENT AND RETENTION

This study will have a goal of 100 evaluable patients. It is the intent of the study team to recruit additional patients to be screened and enrolled if any of the existing patients are lost to follow-up or withdraw consent.

Potential participants will be identified by sites through physician referrals, available recruitment databases, and other methods available to participating sites to identify potential participants. Specific recruitment materials may be developed by the sponsor. In addition, if any site decides to utilize participant-focused materials for recruitment, such materials and a usage plan will be submitted for IRB review and approval prior to implementation. A clinical enrollment manager (CEM) or sponsor designee(s) may locally support the research team and facilitate patient recruitment at the study site in addition to all other measures/efforts. Under no circumstance will referral fees, incentives, or bonuses to physicians for recruitment be allowed.

There is no specific plan to target participants based on race, gender, or age. All eligible potential participants will be approached for inclusion.

It is anticipated that recruitment will take up to 12 months to complete at approximately five research sites. Sites will be NCI-designated cancer centers, academic medical centers, clinics, and doctor's offices within the United States. Sites can include community facilities as a primary site or a satellite site of a participating center as long as they meet the requirements regarding the proper handling and administration of the investigational agent.

Due to the size and short duration of the study, there is no planned retention or compensation plan for participants. Throughout the study, participants will be reminded about upcoming visits and the procedures to be performed at the visit. New information that surfaces during the study will be communicated to participants through IRB-approved mechanisms.

In alignment with the Internal Revenue Service (IRS) 2020 Standard Mileage Rate (Notice 2020-05), participants can be reimbursed at a rate of 17 cents per mile driven in an automobile for traveling for study-related medical purposes. This will be done approximately one month after travel receipts are submitted by study staff to the sponsor.

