9.2 SAMPLE SIZE DETERMINATION

The intent of this study is to enroll approximately 100 evaluable patients to assess the safety of IFx-Hu2.0 as a monotherapy. A sample size of 100 has the following precision for estimation of DLT rates ranging from 0.1 to 0.5. A DLT is defined as an adverse event equal to or greater than grade 3, at least possibly related to the investigational agent, occurring within a 4-week period following IP administration, and deemed as having unacceptable toxicity by the principal investigator and/or medical monitor. Precision is measured by 1-sided 95% upper confidence limit on the estimated DLT rate via exact binomial distribution. For example, if no DLT is observed in patients on IFX-Hu 2.0, then the true underlying DLT rate is lower than 0.099 with 95% confidence.

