9.4 STATISTICAL ANALYSES

9.4.1 GENERAL APPROACH

This is a safety and feasibility study that is designed to evaluate the safety and feasibility of IFx-Hu2.0 use as monotherapy. Safety will be assessed and reported based upon CTCAE v5.0 criteria. Feasibility will be defined as the ability to treat at least 80 of the 100 patients enrolled without dose-limiting toxicity.

The secondary endpoint is Pathological Response defined as a response assessment to IFx-Hu2.0 in tumor lesions excised at four weeks as; pathological complete response (pCR), major pathological response (mPR), partial pathological response (pPR), or pathological non-response (pNR) by evaluating percent Residual Vial Tumor (%RVT)(15).

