2.2 Study Endpoints

2.2.1 Primary Endpoint

The primary endpoints of this trial will be the safety and feasibility of the treatment regimen. Safety will be reported using the most current version of the Common Terminology Criteria for Adverse Events (CTCAE).

Feasibility will be defined as the ability to treat at least 85 of the approximate 100 patients enrolled without investigational product (IP) related dose-limiting toxicity (DLT).

A DLT is defined as an adverse event equal to or greater than grade 3, at least possibly related to the investigational agent, occurring within a 4-week period following IP administration.

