3. STATISTICAL METHODS

3.1 *General*

All data will be analyzed using the Statistical Analysis System (SAS®; Version 9.2 or higher). Continuous variables will be summarized using descriptive statistics, including sample size, mean, standard deviation (SD), median, minimum, and maximum. Categorical variables will be summarized using number and percent of subjects for each outcome.

All statistical tests will be two sided, and statistical significance level is 0.05.

3.2 *Subject Disposition, Demographics and Baseline Characters*

- Reasons for withdrawal will be summarized.
- Demographics and baseline characters will be summarized on safety analysis set using descriptive statistics.
- Medical history will be summarized with MedDRA system organ class (SOC) and preferred term (PT) for Safety analysis set.
- Prior and concomitant medications will be summarized with WHO Drug Class 3 name for Analysis of Study Endpoints

3.2.1 *Safety Analysis*

The safety analysis will be conducted on safety analysis set that includes all treated subjects.

Safety endpoints will be analyzed as summary statistics during treatment and/or as change scores from baselines such as shift tables. Treatment emergent adverse events (TEAEs) will be coded using Medical Dictionary for Regulatory Activities (MedDRA). TEAE severity and relationship to study treatment will be presented by dose cohort, MedDRA system organ class (SOC) and preferred term (PT).

The information reported about each AE will be the start date, stop date, severity, relationship, outcome, and duration). AEs leading to premature discontinuation from the study and serious treatment emergent AEs will be presented with either a summary table or a data listing.

- **Adverse Events**

TEAEs are defined as signs or symptoms that emerge during treatment or within 28 days of the last dose of Investigational Product, including those signs and symptoms that have been absent pre-treatment or that have worsened relative to the pre-treatment assessment. Any adverse event considered related to treatment will also be considered a TEAE, regardless of the elapsed time since the last dose of Investigational Product.

Number and percentage of subject with any DLT will be reported by dose cohort, MedDRA SOC and PT. Overall DLT rate for safety analysis set will be provided with 95%CI.

Number and percentage of subject with any TEAEs will be summarized by MedDRA SOC, PT, intensity, and relationship to the study treatment.

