3.4. Handling of Missing Data

Missing data will not be imputed for safety analyses.

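### Treated patients who leave are replaced, but no DLT-evaluable set is defined: patients lost before Week 4 count as non-events in the DLT rate, and the feasibility count, read literally, does not scale with the number treated

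*Protocol*

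**What the plan says.** - **Replacement.** Protocol 7.2: patients who consent and receive the intervention "and subsequently withdraw, or are withdrawn or discontinued from the study will be replaced". The reason for leaving makes no difference.
- **Target number.** Protocol 5.5: "This study will have a goal of 100 evaluable patients". Protocol 9.2 and SAP 2.3 repeat this goal. None of them defines an evaluable patient.
- **Feasibility.** SAP 2.2.1, like the protocol synopsis: "Feasibility will be defined as the ability to treat at least 85 of the approximate 100 patients enrolled" without an IP-related DLT. Protocol 9.4.1, like protocol section 3, has 80: "ability to treat at least 80 of the 100 patients enrolled without dose-limiting toxicity". Both are counts tied to patients enrolled. The SAP describes no analysis of feasibility.
- **DLT rate.** SAP 3.2.1: "Overall DLT rate for safety analysis set will be provided with 95%CI". SAP 2.1 and 3.7 define that set as everyone who received a dose, with no follow-up requirement.
- **Missing data.** SAP 3.4: "Missing data will not be imputed for safety analyses". No rule covers a patient whose 4-week DLT window is incomplete.
- **Stopping rule.** Protocol 9.4.2 compares the number of DLTs with a boundary indexed by the number of patients who have completed follow-up.

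**The concern.** The DLT is a windowed endpoint: a patient is known to be free of it only after four weeks of observation. Three provisions do not fit together. Recruitment aims at 100 evaluable patients, the final DLT rate is taken over all dosed patients, and feasibility is a count among those enrolled. If L treated patients leave and are replaced, the number treated is 100 + L.

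Two separate effects follow.

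1. A leaver with no recorded DLT is in the denominator of the rate and not in the numerator. No sentence calls such a patient DLT-free, but that is what an all-treated denominator without imputation produces. The same DLT rate is monitored on a different denominator from the one used to report it.
2. If 85 is a plain count, each additional treated patient is another chance to reach it, whether or not that patient is fully observed.

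Both effects favour success. At stake are the primary DLT estimate and its interval, and whether feasibility is declared.

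**Working it through.** **Inputs.** Thresholds of 85 (synopsis, SAP 2.2.1) and 80 (protocol section 3, 9.4.1). 100 evaluable patients (protocol 5.5, 9.2). All-treated denominator (SAP 3.2.1). A DLT rate of 0.20, at which protocol 9.4.2 sets its stopping boundary. Assumed, because the documents give no dropout rate: L treated leavers with an unobserved window and no recorded DLT, with L from 0 to 10, and leaving unrelated to DLT.

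**The plan's own figures.** The boundary in protocol 9.4.2 reproduces: the smallest r with P(X ≥ r | n, 0.2) ≤ 0.008340 matches the table at every n from 1 to 100. The one precision figure in protocol 9.2 does not: zero DLTs in 100 gives an upper limit of 1 − 0.05^(1/100) = 0.0295, not 0.099. That is a separate error, and nothing below depends on it.

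**Effect 1: the DLT rate.** Reported rate = x / (100 + L), here with x = 20 DLTs among the 100 observed patients, and the exact two-sided 95% upper limit:

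| L | Reported rate | Upper limit |
|---|---|---|
| 0 | 20/100 = 20.0% | 0.292 |
| 5 | 20/105 = 19.0% | 0.279 |
| 10 | 20/110 = 18.2% | 0.267 |

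Counting every unobserved leaver as a DLT instead gives 25/105 = 23.8% and 30/110 = 27.3%.

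**Effect 2: feasibility with the 85 threshold, true DLT rate 0.20.**

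- (a) Literal count, leavers scored as non-events. Pass if (100 − X) + L ≥ 85, that is X ≤ 15 + L, with X ~ Bin(100, 0.20).
- (b) Literal count, all 100 + L fully observed. Pass if X ≤ 15 + L, with X ~ Bin(100 + L, 0.20). This isolates the part due to the count not scaling.
- (c) 85% of all treated, leavers scored as non-events. Pass if X ≤ 0.15 × (100 + L) rounded down, with X ~ Bin(100, 0.20). The limit is 15 for L up to 5 and 16 for L = 10.

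| L | (a) | (b) | (c) |
|---|---|---|---|
| 0 | 0.129 | 0.129 | 0.129 |
| 1 | 0.192 | 0.180 | 0.129 |
| 2 | 0.271 | 0.240 | 0.129 |
| 3 | 0.362 | 0.309 | 0.129 |
| 5 | 0.559 | 0.461 | 0.129 |
| 10 | 0.913 | 0.800 | 0.192 |

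At L = 5 the rise under (a) is 0.559 − 0.129 = 0.430. Of this, 0.461 − 0.129 = 0.332, or 77%, appears with no missing follow-up at all.

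**Other settings, reading (a).** With the 80 threshold at 0.20 the chance goes from 0.559 (L = 0) to 0.739 (L = 2) and 0.913 (L = 5). With the 85 threshold it goes from 0.568 to 0.934 (L = 5) at a true rate of 0.15, and from 0.960 to 0.999 (L = 5) at 0.10.

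**Under the proposed definition.** With feasibility stated as a proportion of 100 DLT-evaluable patients, the chance is 0.129 at a rate of 0.20 for any L, as long as leaving is unrelated to DLT.

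**The case against.** The strongest reply is that the large figures depend on one reading. The criterion pairs its numerator with a denominator of about 100, and nothing says that 85 of 110 would pass. It could mean 85% of those treated, or 85 of the 100 evaluable patients; on the latter, leavers unrelated to DLT cause no bias. This stands: the count reading is literal, but it is not the only one. It does not remove the need to choose, because the text says enrolled, replacement moves enrolment above 100, and the SAP gives no feasibility analysis to settle the matter.

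Second, few patients should be unobserved. There is one dose and one 4-week visit, at which the lesion is excised. The schedule includes an early termination visit with AE review. Protocol 7.3 requires repeated contact attempts, and 8.2.4 extends recording to 7 days (AEs) or 30 days (SAEs) after last participation. This limits L, and at L = 0 there is no effect. But 7.3 also provides for patients who cannot be reached, and no rule says how they are scored.

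Third, a true DLT rate of 20% may be pessimistic: the earlier monotherapy trial reported no grade 3 to 5 treatment-related events in six evaluable patients. At 10% the effect on feasibility is small.

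Fourth, an all-treated safety set is conventional, and it correctly keeps DLTs recorded before a patient left. A reader might infer that patients withdrawn for an adverse event, a reason listed in protocol 7.2, drop out of the count. The documents do not support that: such an event is recorded, stays in the all-treated numerator if it is a DLT, and is also presented among AEs leading to discontinuation. The gap concerns patients lost to follow-up or withdrawing consent with no event recorded.

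**Conclusion.** The concern holds as a gap in definition, with two effects of different size. For the DLT rate, unobserved leavers enter as non-events and pull the estimate down by about 1 point with 5 leavers and 1.8 points with 10, when 20 DLTs are observed. For feasibility, the literal count becomes easier to meet as patients are replaced: from 0.13 to 0.27 with 2 leavers and 0.56 with 5, at a true rate of 20% and the 85 threshold. Most of that rise comes from the unscaled count rather than from missing follow-up.

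A reader might go further and conclude that the primary endpoint is biased towards success through unobserved leavers. The documents do not support that as a general statement. The large figures need the literal count, a true rate near 20% and several leavers, and no dropout rate is given. On the proportional reading, the chance is unchanged with 5 leavers and 0.19 with 10. What can be said is that neither effect works against success, that both vanish with no leavers, and that the plan does not say which reading applies. The conflict between 85 and 80 is a separate matter, but it has to be settled before the criterion can be restated.

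**What to change.** In both protocol and SAP:

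1. Define a DLT-evaluable set: treated patients who had a DLT in the 4-week window, or who were followed through it. State whether a final visit early in the ±5-day allowance (Day 23) completes the window. Use this definition for the 100 evaluable patients, and keep a patient with a DLT in the set even if that patient leaves and is replaced.
2. Reconcile 85 and 80, then state feasibility as a proportion of this set, and add its analysis to the SAP.
3. Report the DLT rate and its confidence interval on this set, which brings the final analysis close to the stopping rule's denominator.
4. Keep the all-treated rate as supportive, with a sensitivity analysis counting unobserved leavers as DLTs, and report how many there were.

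The cost is a wording change in the protocol as well as the SAP, because feasibility is a primary endpoint defined in the protocol, and one population flag. No new visits or data are needed. The DLT rate may look slightly less favourable.
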